5.3.4 Anemia

Symptomatic anemia should be treated with red blood cell transfusion and is recommended if the hemoglobin falls below 8 g/dL. The initiation of erythropoietic therapy for the management of chemotherapy-induced anemia follows the American Society of Hematology/ASCO clinical practice guidelines (http://www.asco.org).

5.3.5 Thrombocytopenia

Thrombocytopenia will be treated conservatively. In the absence of bleeding, or a necessary invasive procedure, platelet transfusions should be given for a platelet

count $\leq 10,000/\text{mm}^3$. If invasive procedure(s) is (are) planned, or the patient develops bleeding, platelet transfusions should be administered in accordance with the standard of practice, usually maintaining a platelet count above 50,000/mm³.

5.4 **Duration of Therapy**

In the absence of treatment delays due to adverse events, treatment may continue until one of the following criteria applies:

- Disease progression
- Intercurrent illness that prevents further administration of treatment
- Significant toxicity occurs despite 2 dose reductions as described in Section 6 or no lower dose level exists
- Pregnancy
- Patient decides to withdraw from the study, or
- General or specific changes in the patient's condition render the patient unacceptable for further treatment in the judgment of the investigator

5.5 **Duration of Follow Up**

Patients will be followed for 30 days after the last dose is administered or until one of the following occurs: patient enrolls on another protocol, patient receives standard of care, or death, whichever comes first. The follow-up will consist of a phone call between Days 27-30 after the last dose to evaluate adverse events that were ongoing and any new events that might be deemed related to the therapy. Toxicities felt to be possibly, probably, or definitely related to the study drugs that have not resolved or stabilized by Day 30 post-treatment will be followed until stabilization or resolution via phone calls as clinically indicated. An optional biopsy from patients who have progressed may be requested if the patient has not yet received any new treatment to assess whether progression correlates with a change in study pharmacodynamic marker; separate consent will be obtained.

5.6 Criteria for Removal from Study

Patients will be removed from study for one of the following reasons: completed 30-day follow up period or toxicities are unresolved but stabilized, patient enrolls on another protocol, or patient receives standard of care. The reason for study removal and the date the patient was removed must be documented in the medical record and communicated to Central Registration per Section 4.

6 DOSING DELAYS/DOSE MODIFICATIONS

Toxicities should have resolved to \leq Grade 2 prior to starting the next cycle. Treatment may be delayed for a maximum of 2 weeks beyond the actual cycle length of 21 days for toxicities that develop and do not resolve as defined above. Beyond two weeks, the patient will not receive further therapy on this protocol and will be followed for resolution of toxicities. Treatments may be delayed up to 7 days past the end of the previous cycle of 21 days for scheduling conflicts at the discretion of the investigator.

Patients will be allowed up to 2 dose reductions. If more than 2 dose reductions are required, the patient will be removed from the study.

6.1 Dose Reduction

Dose modifications are defined below:

- **6.1.1 Grade 2 Drug-related toxicity**: No changes will be made to the dose of AZD1775 for Grade 2 toxicities. Therapy will not be interrupted for Grade 2 hematologic toxicities.
- 6.1.2 Grade 3-4 Drug-related non-hematologic toxicities: Doses of AZD1775 will be held until toxicities recover to \leq Grade 2 or baseline prior to re-initiating treatment at the next lower dose level. Electrolyte abnormalities will not require dose reduction if resolution to Grade 2 or less is documented within 72 hours. Dose modifications for nausea, vomiting, and diarrhea will be made only if they are refractory to treatment (See Section 5.3).
- **6.1.3** Grade 3 Drug-related hematologic toxicities: Dose of AZD1775 will be held until hematologic toxicities, except anemia, lymphopenia, or leukopenia in the absence of neutropenia, have resolved to \leq Grade 2 prior to re-initiating treatment at the same dose level.
- **6.1.4** Grade 4 Drug-related Hematologic Toxicities: Dose of AZD1775 will be held until hematologic toxicities, except anemia, lymphopenia, or leukopenia in the absence of neutropenia, have resolved to \leq Grade 2 prior to re-initiating treatment at the next lower dose level.

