5.2.1 Grade \geq 3 Non-Hematological Toxicity

Grade \geq 3 non-hematological toxicity felt to be related to study medications will be considered dose-limiting with the following clarifications:

5.2.1.1 Diarrhea Grade 3 will only be considered dose-limiting if it is refractory to treatment as outlined in Section 5.3.2, Supportive Care Guidelines, and unable to be corrected to Grade 2 or less within 24 hours. Bloody or Grade 4 diarrhea will be dose-limiting.

5.2.1.2 Nausea and vomiting Grade 3 will only be considered dose-limiting if it is refractory to anti-emetic therapy and unable to be corrected to Grade 1 or less within 24 hours (Section 5.3.1).

5.2.1.3 Rise in creatinine to Grade 3, not corrected to Grade 1 or less within 48 hours with IV fluids will be considered dose-limiting. All Grade 4 rises in creatinine will be dose limiting.

5.2.1.4 Grade \geq 3 metabolic toxicities unable to be corrected to Grade 1 or baseline within 48 hours (hypocalcemia or hypercalcemia, hypomagnesemia or hypermagnesemia, and hyponatremia) will be considered dose limiting. For hypokalemia or hyperkalemia, grade \geq 2 toxicities unable to be corrected to grade 1 or less within 48 hours will be considered dose limiting. Grade 4 metabolic toxicities that are symptomatic will be considered dose-limiting regardless of duration or ability to correct.

- **5.2.2** Grade 4 thrombocytopenia or Grade 3 thrombocytopenia associated with bleeding.
- **5.2.3** Grade 4 neutropenia \geq 5 days or febrile neutropenia.
- **5.2.4** Any degree of anemia, leukopenia in the absence of grade 4 neutropenia \geq 4 days, or lymphopenia will not be considered dose limiting.
- 5.2.5 Any degree of alopecia will not be considered dose limiting.
- 5.2.6 Grade 3 fatigue of greater than 1 week duration.
- 5.2.7 Failure to tolerate 100% of the dosing in the first cycle will be considered a DLT.

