5.3.2 Diarrhea

If diarrhea develops and does not have an identifiable cause other than study drug administration, anti-diarrheals such as Lomotil (diphenoxylate HCl 2.5 mg + atropine sulfate 0.025 mg/tablet) dosed according to package insert or loperamide 4 mg po after the first unformed stool with 2 mg po with every 2 hours as long as unformed stools continue (4 mg every 4 hours while asleep). No more than 16 mg of loperamide should be taken during a 24-hour period. This regimen can be repeated for each diarrheal episode. Diarrhea will be considered refractory if it does not resolve within 24 hours \leq to Grade 2 with the above regimen (maximum of 16 mg of loperamide in a 24-hour period). If the patient develops blood or mucus in the stool, dehydration, or hemodynamic instability, or fever along with the diarrhea, anti-diarrheals will be discontinued and the patient will be treated with IV fluids and antibiotics as medically indicated.

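### Section 6.1 lets two serious events that Section 5.2 calls dose-limiting be re-treated with no dose reduction: Grade 3 thrombocytopenia with lower-grade bleeding, and Grade 4 diarrhea that responds within a day

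*Combined protocol and SAP*

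**What the plan says.** Two sets of rules apply to the same events. Section 5.2 defines DLT in the first cycle and drives cohort escalation. Section 6.1 sets the dose at which an individual patient resumes, in any cycle.

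- **Platelets.** Section 5.2.2 lists as a DLT "Grade 4 thrombocytopenia or Grade 3 thrombocytopenia associated with bleeding". Under 6.1.3, Grade 3 related hematologic toxicity is held until Grade 2 or less "prior to re-initiating treatment at the same dose level". Its only carve-outs are anemia, lymphopenia, and leukopenia without neutropenia.
- **Diarrhea.** Section 5.2.1.1 states: "Bloody or Grade 4 diarrhea will be dose-limiting". Section 6.1.2 states: "Dose modifications for nausea, vomiting, and diarrhea will be made only if they are refractory to treatment". The test is in 5.3.2: "Diarrhea will be considered refractory if it does not resolve within 24 hours" to Grade 2 or less on the anti-diarrheal regimen. If blood appears in the stool, the same section says that "anti-diarrheals will be discontinued and the patient will be treated with IV fluids and antibiotics as medically indicated".

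Section 6 allows at most two dose reductions and a delay of at most two weeks beyond the 21-day cycle. Section 5.4 lets the investigator stop treatment on judgment.

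**The concern.** Section 6.1 already steps the dose down after many DLTs: Grade 4 thrombocytopenia under 6.1.4, and Grade 3 fatigue lasting over a week or refractory Grade 3 vomiting under 6.1.2. A patient whose platelet fall came with bleeding, or who had Grade 4 diarrhea, has had an event that the protocol ranks with these, yet the text returns that patient to the dose that caused it. The documents give no reason for the difference.

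An event that triggers no reduction also never counts toward the two-reduction limit, so a recurrence can be re-treated at the same dose again. After cycle 1, routine blood counts and chemistry are scheduled only around the start of each cycle (Section 5; Section 10, footnote c), so there is little scheduled monitoring within a cycle to offset an unchanged dose.

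**Working it through.** The plan states no figure on this point, so there is none to reproduce. The check sets each DLT rule beside the dose rule for the same event, then sizes the reduction that is missing.

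**Step 1: the rules side by side**

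| Related event | DLT under 5.2? | Dose on resuming under 6.1 |
|---|---|---|
| Grade 4 thrombocytopenia | Yes (5.2.2) | Next lower level (6.1.4) |
| Grade 3 thrombocytopenia, no bleeding | No | Same level (6.1.3) |
| Grade 3 thrombocytopenia, bleeding below Grade 3 | Yes (5.2.2) | **Same level (6.1.3)** |
| Grade 3 thrombocytopenia, related bleeding of Grade 3-4 | Yes | Next lower level, through the bleeding event (6.1.2) |
| Grade 3 diarrhea, refractory, no blood | Yes (5.2.1.1) | Next lower level (6.1.2) |
| Grade 4 diarrhea, not at Grade 2 or less by 24 hours | Yes | Next lower level (6.1.2) |
| Grade 4 diarrhea, Grade 2 or less by 24 hours | Yes (5.2.1.1) | **No modification (6.1.2 with 5.3.2)** |
| Bloody Grade 3 diarrhea | Yes (5.2.1.1) | **Not determinable** |

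The last row differs in kind from the other two in bold. The text does not bar a reduction there. It makes the reduction depend on failure of a regimen that 5.3.2 has just stopped. Gastrointestinal hemorrhage recorded as its own related Grade 3-4 event is already reduced under 6.1.2 and is outside the point.

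**Step 2: does any other text set a lower dose?**

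- Section 6 requires recovery to Grade 2 or less before the next cycle and limits the delay. It governs when treatment resumes, not at what dose.
- Section 5.4 refers back to the Section 6 reductions and adds investigator judgment to stop. It offers no lower dose.
- Sections 5.1.1, 5.2 and 13.2 use DLT for evaluability, cohort escalation, escalation within a patient, and the MTD. They do not set a patient's dose after a DLT.

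**Step 3: size of the missing reduction at the MTDs**

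Inputs are the dose tables in 5.1.1 and 5.1.2 and the MTDs in Section 5 (Arm A 225 mg twice daily, 5 doses a week for 2 weeks; Arm B 300 mg once daily, 5 days a week for 2 weeks).

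Dose per cycle = mg per dose × doses per cycle. Change = (new − MTD) / MTD.

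- Arm B, MTD (level 4): 300 × 10 = 3000 mg.
  - First reduction (level 3): 250 × 10 = 2500 mg; −500/3000 = −16.7%.
  - Second reduction (level 2): 225 × 10 = 2250 mg; −750/3000 = −25.0%.
- Arm A, MTD (level 2): 225 × 10 = 2250 mg.
  - First reduction (level 1): 225 × 5 = 1125 mg; −1125/2250 = −50.0%.
  - Second reduction (level −1): 200 × 5 = 1000 mg; −1250/2250 = −55.6%.

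Arm B has four levels below its MTD (3, 2, 1, −1) and Arm A has two (1, −1), so both allowed reductions exist in each arm.

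**The case against.** The strongest objection is that the two sections serve different purposes. Section 5.2 governs escalation, 6.1 governs continuing patients, and no text says that a DLT must lower that patient's dose. This stands. The point therefore cannot rest on a general rule that every DLT needs a reduction. It rests on the result for these two events.

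It can also be said that the refractory condition in 6.1.2 is explicit policy, as explicit as the neighboring 72-hour exception for electrolytes. That is fair for Grade 4 diarrhea that responds: the text is clear, and the criticism is of the choice. It does not help with bloody diarrhea, where the test fails. For platelets there is no exception sentence at all; the same-dose restart simply follows from the grade.

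Safeguards exist: the hold until recovery, the two-week limit, the right to stop, and the reduction when bleeding is itself Grade 3-4. They narrow the gap without supplying a lower dose. An investigator who lowered the dose after Grade 3 thrombocytopenia with minor bleeding would be departing from 6.1.3.

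A reader might add Grade 2 potassium toxicity. Section 5.2.1.4 says of Grade 2 or higher events that "toxicities unable to be corrected to grade 1 or less within 48 hours will be considered dose limiting", while 6.1.1 says "No changes will be made to the dose of AZD1775 for Grade 2 toxicities". The wording does differ, but the documents do not support calling it a safety gap. Section 6 accepts Grade 2 for starting the next cycle, and 6.1.2 requires no reduction for a Grade 3-4 electrolyte event that is back to Grade 2 within 72 hours. Reducing the dose for a patient who never exceeded Grade 2 would put the stricter rule on the milder event.

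**Conclusion.** The point holds for two events. After Grade 3 thrombocytopenia with bleeding below Grade 3, the protocol directs a restart at the same dose. After Grade 4 diarrhea that reaches Grade 2 or less within 24 hours, it rules out a dose change. A related gap is that bloody Grade 3 diarrhea has no usable rule. It is worth correcting for the safety of patients who continue treatment, including those in Expansion Arm B (up to 20, with accrual stopping at 10 usable biopsy pairs).

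A reader might infer that 6.1 works by grade alone and disregards dose-limiting events generally. The text does not bear that out. Section 6.1.2 also uses refractoriness and a 72-hour window, and most of the severe DLTs compared above already lead to a reduction.

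Nor does the point touch the trial's conclusions on dose: the MTDs and DLT counts depend on 5.2 only. The documents give no frequency for these events, so the number of patients affected cannot be estimated. The conclusion assumes that the events are attributed to AZD1775 and that 5.3.2 supplies the meaning of refractory in 6.1.2, which refers to Section 5.3 for it.

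**What to change.** Add two sentences, written by event and applying in any cycle.

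- In 6.1.3: *Grade 3 thrombocytopenia with bleeding restarts at the next lower dose level after recovery to Grade 2 or less.*
- In 6.1.2: *Bloody Grade 3 diarrhea and any Grade 4 diarrhea restart at the next lower dose level after recovery to Grade 2 or less or baseline, whether or not refractory.*

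Leave 6.1.1, the 72-hour electrolyte exception and the Section 6 recovery threshold unchanged.

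No added patients or tests are needed. The cost falls on the affected patients. At the MTDs the first step down removes 16.7% of the dose per cycle in Arm B and 50% in Arm A, where it takes the form of one dosing week instead of two. It uses one of the two allowed reductions. A patient who has none left, or is already at the lowest level, would come off treatment where the present text lets treatment continue. The Arm A step is large and should be accepted knowingly.

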6.2 Definition of Complete Course

A cycle is defined as 21 days, with D1 starting the first day of AZD1775 administration. If a patient receives 90% of scheduled treatments of AZD1775 and remains in the study until D21, the patient will be considered to have completed a cycle of therapy. Patients who do not complete a cycle of therapy for reasons other than toxicity will be replaced. Patients who do not complete one cycle of therapy due to toxicity will not be replaced. All patients should have completed one cycle of therapy (unless removed from the study due to toxicity), at which point they will be evaluable.

7 ADVERSE EVENTS: LIST AND REPORTING REQUIREMENTS

Adverse event (AE) monitoring and reporting is a routine part of every clinical trial. The following list of AEs (Section 7.1) and the characteristics of an observed AE (Section 7.2) will determine whether the event requires expedited reporting (via CTEP-AERS) in addition to routine reporting.

7.1 Comprehensive Adverse Events and Potential Risks list (CAEPR)

The Comprehensive Adverse Events and Potential Risks list (CAEPR) provides a single list of reported and/or potential adverse events (AE) associated with an agent using a uniform presentation of events by body system. In addition to the comprehensive list, a subset, the Specific Protocol Exceptions to Expedited Reporting (SPEER), appears in a separate column and is identified with bold and italicized text. This subset of AEs (SPEER) is a list of events that are protocol specific exceptions to expedited reporting to NCI (except as noted below). Refer to the 'CTEP, NCI Guidelines: Adverse Event Reporting Requirements'

http://ctep.cancer.gov/protocolDevelopment/electronic_applications/docs/aeguidelines.pdf for further clarification. *Frequency is provided based on 313 patients*. Below is the CAEPR for AZD1775 (adavosertib).

NOTE: Report AEs on the SPEER **ONLY IF** they exceed the grade noted in parentheses next to the AE in the SPEER. If this CAEPR is part of a combination protocol using multiple investigational agents and has an AE listed on different SPEERs, use the lower of the grades to determine if expedited reporting is required.

Version 2.6, May 14, 2019¹

¹This table will be updated as the toxicity profile of the agent is revised. Updates will be distributed to all Principal Investigators at the time of revision. The current version can be obtained by contacting [contact]. Your name, the name of the investigator, the protocol and the agent should be included in the e-mail.

²Gastrointestinal hemorrhage includes Anal hemorrhage, Cecal hemorrhage, Colonic hemorrhage, Duodenal hemorrhage, Esophageal hemorrhage, Esophageal varices hemorrhage, Gastric hemorrhage, Hemorrhoidal hemorrhage, Ileal hemorrhage, Intra-abdominal hemorrhage, Jejunal hemorrhage, Lower gastrointestinal hemorrhage, Oral hemorrhage, Pancreatic hemorrhage, Rectal hemorrhage, Retroperitoneal hemorrhage, and Upper gastrointestinal hemorrhage under the GASTROINTESTINAL DISORDERS SOC.

³Infection includes all 75 sites of infection under the INFECTIONS AND INFESTATIONS SOC.

⁴Rash may include rash, erythema, eczema, and rash maculo-papular.

⁵Peripheral neuropathy includes both peripheral motor neuropathy and peripheral sensory neuropathy.

⁶Acute kidney injury includes renal impairment and acute renal insufficiency.

BLOOD AND LYMPHATIC SYSTEM DISORDERS - Blood and lymphatic system disorders -Other (pancytopenia); Blood and lymphatic system disorders - Other (thrombocytosis); Leukocytosis **CARDIAC DISORDERS** - Cardiac disorders - Other (cardiomegaly); Chest pain - cardiac; Myocardial infarction; Palpitations; Sinus bradycardia; Sinus tachycardia

EAR AND LABYRINTH DISORDERS - Ear pain; Hearing impaired; Tinnitus **EYE DISORDERS** - Blurred vision; Cataract; Eye disorders - Other (eye swelling); Eye pain; Keratitis; Photophobia; Scleral disorder; Vision decreased; Watering eyes

GASTROINTESTINAL DISORDERS - Abdominal distension; Anal pain; Ascites; Belching; Bloating; Cheilitis; Colonic obstruction; Dry mouth; Duodenal ulcer; Dysphagia; Enterocolitis; Flatulence; Gastric ulcer; Gastritis; Hemorrhoids; Oral pain; Rectal pain; Small intestinal obstruction

GENERAL DISORDERS AND ADMINISTRATION SITE CONDITIONS - Chills; Death NOS; Edema trunk; Flu like symptoms; Gait disturbance; General disorders and administration site conditions - Other (catheter site pain); Infusion site extravasation; Malaise; Non-cardiac chest pain; Pain

IMMUNE SYSTEM DISORDERS - Allergic reaction; Anaphylaxis; Cytokine release syndrome **INJURY, POISONING AND PROCEDURAL COMPLICATIONS** - Fall; Injury, poisoning and procedural complications - Other (excoriation); Injury, poisoning and procedural complications -Other (ligament sprain)

INVESTIGATIONS - Alkaline phosphatase increased; Aspartate aminotransferase increased; Blood bilirubin increased; Creatinine increased; GGT increased; Investigations - Other (blood urea increased); Lymphocyte count increased; Weight loss

METABOLISM AND NUTRITION DISORDERS - Alkalosis; Hypercalcemia; Hyperglycemia; Hyperkalemia; Hyperuricemia; Hypoalbuminemia; Hypocalcemia; Hyponatremia; Hypophosphatemia; Tumor lysis syndrome

MUSCULOSKELETAL AND CONNECTIVE TISSUE DISORDERS - Arthralgia; Arthritis; Bone pain; Flank pain; Generalized muscle weakness; Muscle cramp; Muscle weakness lower limb; Musculoskeletal and connective tissue disorder - Other (groin pain); Neck pain; Pain in extremity

NEOPLASMS BENIGN, MALIGNANT AND UNSPECIFIED (INCL CYSTS AND POLYPS) -Neoplasms benign, malignant and unspecified (incl cysts and polyps) - Other (carcinoid tumor); Tumor pain

NERVOUS SYSTEM DISORDERS - Central nervous system necrosis; Cognitive disturbance; Dysesthesia; Dysgeusia; Encephalopathy; Lethargy; Nervous system disorders - Other (hemiparesis); Paresthesia; Peripheral neuropathy⁵; Presyncope; Somnolence; Syncope

PSYCHIATRIC DISORDERS - Agitation; Anxiety; Confusion; Depression

RENAL AND URINARY DISORDERS - Acute kidney injury⁶; Hematuria; Urinary frequency; Urinary incontinence; Urinary retention; Urinary tract pain

REPRODUCTIVE SYSTEM AND BREAST DISORDERS - Genital edema; Reproductive system and breast disorders - Other (female genital tract fistula)

RESPIRATORY, THORACIC AND MEDIASTINAL DISORDERS - Allergic rhinitis; Bronchopulmonary hemorrhage; Epistaxis; Hiccups; Nasal congestion; Pleural effusion; Pneumonitis; Pulmonary hypertension; Respiratory, thoracic and mediastinal disorders - Other (diaphragmalgia); Voice alteration; Wheezing

SKIN AND SUBCUTANEOUS TISSUE DISORDERS - Alopecia; Bullous dermatitis; Dry skin; Hyperhidrosis; Pain of skin; Palmar-plantar erythrodysesthesia syndrome; Pruritus; Purpura; Rash acneiform; Skin ulceration; Urticaria

VASCULAR DISORDERS - Flushing; Hematoma; Hot flashes; Hypertension; Hypotension; Thromboembolic event

Note: AZD1775 (adavosertib) in combination with other agents could cause an exacerbation of any adverse event currently known to be caused by the other agent, or the combination may result in events never previously associated with either agent.

7.2 Adverse Event Characteristics

- **CTCAE term (AE description) and grade:** The descriptions and grading scales found in the revised NCI Common Terminology Criteria for Adverse Events (CTCAE) version 4.0 will be utilized for AE reporting until March 31, 2018. CTCAE version 5.0 will be utilized for AE reporting beginning April 1, 2018. All appropriate treatment areas should have access to a copy of the CTCAE version 5.0. A copy of the CTCAE version 5.0 can be downloaded from the CTEP web site http://ctep.cancer.gov/protocolDevelopment/electronic_applications/ctc.htm.
- **'Expectedness'**: AEs can be 'Unexpected' or 'Expected' (see Section 7.1 above) for expedited reporting purposes only. 'Expected' AEs (the ASAEL) are *bold and italicized* in the CAEPR (Section 7.1).
- **Attribution** of the AE:
 - *1*. Definite The AE *is clearly related* to the study treatment.
 - 2. Probable The AE is likely related to the study treatment.
 - 3. Possible The AE may be related to the study treatment.
 - 4. Unlikely The AE is doubtfully related to the study treatment.
 - 5. Unrelated The AE *is clearly NOT related* to the study treatment.

